### **5.3 Risks and Benefits**

Risk management principles have been applied to both the planning and the intended conduct of the clinical investigation, in order to ensure the reliability of the clinical data generated and the safety of the subjects. The clinical investigation process risks are managed through appropriate training and monitoring according to the protocol-specific monitoring plan. Investigational device risks, including risks associated with use of device and methods and procedures for application of device, are defined in the investigator's brochure and/or product labeling and are managed through review of safety assessments outlined in this protocol.

Contact lenses may offer improved peripheral vision and the convenience of not wearing spectacles. Material properties and design characteristics of serafilcon A contact lenses are features consistent for successful contact lens wear. Based upon nonclinical testing and documented rationale for applicability of test results, LID226397 contact lenses, which is made of the same material as Alcon serafilcon A sphere contact lens, are assessed to be nontoxic and biocompatible for on-eye use.

In the US, Acuvue Oasys contact lenses have approved indications for use for both daily wear and extended wear for up to 6 continuous nights. Further details on any known potential risks and benefits can be found in the product package insert.

A summary of the known potential benefits and risks associated with LID226397 contact lenses can be found in the IB. The potential harms associated with on-eye exposure to the new lens materials include toxicity response, blurred vision, and ocular discomfort. In general, when worn for daily wear, the risks with LID226397 contact lenses are anticipated to be similar to other marketed soft contact lenses worn for daily wear.

There may also be unknown risks to use of LID226397 contact lenses. Any risk to subjects in this clinical study will be minimized by compliance with the eligibility criteria and study procedures, clinical oversight, and monitoring. Site personnel will educate subjects on proper hygiene and lens handling, and compliance with the use of contact lenses for daily wear according to the protocol. Subjects should be instructed not to wear contact lenses while

swimming due to increased risk of infection, or while sleeping. Site personnel should advise the subjects to remove contact lenses and return for prompt follow-up of symptoms such as ocular discomfort, foreign body sensation, excessive tearing, vision changes, or hyperemia.

Refer to the IB for additional information.

## 6 STUDY OBJECTIVES

[figure not shown]
### 6.1 Primary Objective(s)

[figure not shown]
**Table 6–1 Primary Objective(s)**

Objective(s)	Endpoint(s)
To evaluate the percentage of LID226397 contact lenses with axis orientation within $\pm 30$ degrees from the 90° axis (ideal location), 10 min after lens insertion at dispense visit.	Percent of lenses with axis orientation within $\pm 30$ degrees from the intended axis, 10 min after insertion

### 6.2 Secondary Objective(s)

Not applicable.

## 6.4 Safety Objective(s)

**Table 6-3 Safety Objective(s)**

Objective(s)	Endpoint(s)
To describe the safety profile of the study products	

• Adverse events

• Biomicroscopy findings

• Device deficiencies

## 7 INVESTIGATIONAL PLAN

### 7.1 Study Design

This is a prospective, randomized [REDACTED] bilateral, crossover, controlled, double-masked, multicenter clinical study, evaluating the LID226397 and AOfAHP contact lenses, to be conducted at approximately 6 sites.

Subjects will be randomized to 1 of 2 crossover sequences, [REDACTED] [REDACTED] and exposed to test and comparator lenses for bilateral wear. Subjects will be expected to complete all 7 scheduled visits. Subjects will be asked to wear their habitual spectacles only (no contact lens wear) during the washout periods for 3 to 4 days after Visit 1, and for 2 (at least 48 hours) to 4 days after Visit 4. All study contact lenses will be prescribed according to subject's prescription and fitted using the manufacturers fitting instructions. Investigator will insert the contact lenses with scribe mark in the direction of the intended 6 o'clock position (90° axis), [REDACTED] [REDACTED].

This is a double masked study design where both the investigator and the subjects will be masked to the details of the study products and assigned treatment (lens) sequences. Differences in scribe marks and lens thickness profile between the study lenses could result in potential inadvertent unmasking of investigator. [REDACTED]  
[REDACTED]  
[REDACTED]  
[REDACTED]  
[REDACTED]  
[REDACTED]

Subjects will be provided with CLEAR CARE Cleaning & Disinfecting Solution to use with the study lenses for the duration of study. LacriPure saline will be permitted for rinsing the lens(es) after removal and prior to insertion, if required.

## 7.2 Rationale for Study Design

This study design is justified based upon an evaluation of the results of relevant preclinical and clinical testing, as described within the IB.

The investigational contact lens is intended for the optical correction of refractive ametropia (myopia or hyperopia, with astigmatism) in persons with non-diseased eyes.

The purpose of this study is to evaluate the on-eye clinical performance of investigational LID226397 contact lenses to support contact lens product development and to evaluate product performance in the intended population. [REDACTED]

The primary and [REDACTED] endpoints were selected to fulfill the primary [REDACTED] objectives of the study. Procedures for measurement of these endpoints were selected based on common practice for these assessments. The design of this study is justified based upon preclinical and clinical testing, as described within the investigator's brochure. [REDACTED]

[REDACTED] AOfAHP contact lenses were chosen as the comparator product

because these lenses also are reusable contact lenses and have the comparable wear modality and same indication for correction of astigmatism (see Package Insert for AOHP contact lenses).

The intended use of this contact lens is vision correction in astigmatism; therefore, the measurement of lens axis orientation, 10 min after insertion is planned as the primary effectiveness endpoint. [REDACTED]

The crossover design will ensure that the same subject is exposed to both the test and comparator lens materials; therefore, [REDACTED] objective assessments [REDACTED] will be obtained for both lenses from the same subject.

[REDACTED]

[REDACTED] The study will exclude any current/habitual AOfAHP lens and daily disposable contact lens wearers, and any previous wearers of AOfAHP or daily disposable contact lenses in the past 3 months prior to consent in order to reduce potential bias of wearers to their habitual contact lenses. There are no immediate plans to submit the results of this pivotal study for publication; however, the results may be offered for publication if they are of scientific interest, or if the results relate to a product that is subsequently approved or cleared for marketing.

### **7.2.1 Purpose and Timing of Interim Analyses and Resulting Design Adaptations**

Interim analyses will not be performed.

### **7.3 Rationale for Duration of Treatment/Follow-Up**

Subjects will wear each study product bilaterally for their respective wear cycles on a daily wear modality. [REDACTED]

[REDACTED] The lenses will be provided by a qualified unmasked study staff member in such a manner that the subject and the investigator remain masked to the lens type. The primary [REDACTED] endpoints will be assessed on dispense visits [REDACTED] respectively. [REDACTED]

 The duration of use of each study product is in accordance with the respective product labeling (see package inserts for AOHP contact lenses and IB for LID226397 contact lenses).

#### **7.4 Rationale for Choice of Comparator Product**

[figure not shown]
AOfAHP contact lenses were chosen as the comparator product because these lenses also are reusable contact lenses (see Package Insert for AOHP contact lenses) and have similar indications for correction of astigmatism.

#### **7.5 Data Monitoring Committee**

Not applicable.

### **8 STUDY POPULATION**

The study population consists of male and female subjects aged 18 or over and who wear any commercial soft toric contact lenses (excluding AOfAHP habitual lens wearers and habitual daily disposable lens wearer) in both eyes with at least 3 months wearing experience, with a minimum wearing time of 5 days per week and 10 hours per day.

The study population will include approximately 92 volunteer subjects to be enrolled (consented) at approximately 6 sites within the US, with a target of 80 total completed subjects. Site-specific targets may vary based upon individual site capabilities. Estimated time needed to recruit subjects for the study is approximately 4 weeks; however, unanticipated circumstances may shorten or lengthen this time and would not require amendment of this protocol. A 15% screening failure rate is expected requiring approximately 92 subjects are expected to be enrolled.

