Device Deficiency	
Inadequacy of a medical device with respect to its identity, quality, durability, reliability, usability, safety, or performance.
 
Note: This definition includes malfunctions, use errors, and inadequacy in the information supplied by the manufacturer including labelling related to the investigational medical device or the comparator.
 
Requirements for reporting Device Deficiencies in the study can be found in Section 11.

Enrolled Subject	Any subject who signs an informed consent form for participation in the study.
Point of Enrollment	The time at which, following recruitment and before any clinical investigation-related procedures are undertaken, a subject signs and dates the informed consent form.
Interventional Clinical Trial	A pre- or postmarket clinical investigation where the assignment of a subject to a particular medical device is decided in advance by a clinical investigation plan, or diagnostic or monitoring procedures requested in the CIP are in addition to those available as normal clinical practice and burden the subject.
Investigational Product	A preventative (vaccine), a therapeutic (drug or biologic), device, diagnostic, or palliative used as a test or comparator

	product in a clinical trial, including a product with a marketing authorization when used or assembled (formulated or packaged) in a way different from the authorized form, or when used for an unauthorized indication, or when used to gain further information about the authorized form.
Malfunction	Failure of an investigational medical device to perform in accordance with its intended purpose when used in accordance with the instructions for use or clinical investigation plan (CIP), or investigator’s brochure (IB).
Noninterventional Study	Clinical investigation that draws inferences about the possible effect of an intervention on subjects, but the investigator has not assigned subjects into intervention groups based on a protocol and has not made any attempts to collect data on variables beyond those available throughout the course of normal clinical practice and burden to the subject.  NOTE: The term “noninterventional” is synonymous with “observational.”
Nonserious Adverse Event	Adverse event that does not meet the criteria for a serious adverse event.

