## 8.1 Inclusion Criteria

Written informed consent must be obtained before any study specific assessment is performed. Upon signing informed consent, the subject is considered enrolled in the study.

Subjects eligible for inclusion in this study must fulfill **all** of the following criteria:

1. Subject must be at least 18 years of age.
2. Subject must be able to understand and must sign an informed consent form (ICF) that has been approved by an Institutional Review Board (IRB/IEC).
3. Successful wearers of any commercial toric soft contact lenses (except AOfAHP and daily disposable lenses) in both eyes with at least 3 months wearing experience, with a minimum wearing time of 5 days per week and 10 hours per day.
4. BCVA distance (as determined by manifest refraction at screening) 20/25 or better in each eye with a sphero-cylindrical refractive error within the available study lens parameter range in the study.

Note: Study lens parameters available in this study are:

-0.75 D and -1.25 D cylinder power with:

- (a) -0.25 to -4.00 D (in 0.25 D steps) spherical power in 10°, 90°, 170° and 180° axis as available
- (b) -5.00 to -10.00 D (in 1 D steps), -5.50 D & -6.50 D spherical power in 90° and 180° axis as available
- (c) +1.00 to +8.00 D (in 1 D steps) spherical power 90° and 180° axis as available

5. Distortion-free keratometric readings at screening

6. Subject must possess spectacles (with 0.3 logMAR or better vision OU) and be willing to wear habitual spectacles for vision correction when study lenses are not worn, as needed.
7. Subject must be willing to stop wearing their habitual contact lenses for the duration of study participation.

9. Willing to NOT use rewetting/lubricating drops at any time during the study.
10. Subjects must be willing and able to attend all scheduled visits.

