## **10.4 Discontinued Subjects**

### **10.4.1 Screen Failures**

Subjects who were excluded from the study after signing the informed consent and prior to randomization to product/dispense of study product.

The investigator must document the reason for screen failure in the subject's case history source documents.

Subject numbers must not be reused.

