#### **12.4.1.1 Statistical Hypotheses**

No inferences are to be made on the primary effectiveness endpoint; therefore, no hypotheses are formulated.

[figure not shown]

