Clinical Performance Evaluation of Two Frequent
Replacement
Silicone Hydrogel Toric Contact Lenses

STUDY ID
CLN109-C001

[figure not shown]
STATISTICAL ANALYSIS PLAN

NCT05959200

Statistical Analysis Plan for CLN109-C001

**Title: Clinical Performance Evaluation of Two Frequent Replacement
Silicone Hydrogel Toric Contact Lenses**

This version of the Statistical Analysis Plan is based on Version 3.0 of the study protocol.

[figure not shown]
Executive Summary:

Key Objectives:

To evaluate the percentage of Alcon serafilcon A Toric (LID226397) contact lenses with axis orientation within ± 30 degrees from the 90° axis (ideal location), 10 minutes (min) after lens insertion at dispense visit.

Decision Criteria for Study Success:

Decision criteria for study success are not applicable for this study.

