1.2 Study Description

Key components of the study are summarized in Table 1-1.

Table 1-1 Study Description Summary

[figure not shown]
| | |
|------------------|---|
| Study Design | Prospective, randomized [REDACTED], bilateral, crossover, controlled, double-masked, multicenter. |
| Study Population | Volunteer subjects aged 18 or over who are habitual soft toric contact lens wearers (excluding AOfAHP habitual lens wearers and habitual daily disposable lens wearers) with normal eyes (other than correction for refractive error). Subjects should have at least 3 months wearing experience, wear these lenses at least 5 days per week and at least 10 hours per day. |

| | |
|------------------------------|---|
| | Target to complete: 80 Planned to enroll: ~92 |
| Number of Sites | ~6 United States |
| Test Product(s) | Alcon serafilcon A toric contact lenses (serafilcon A; LID226397) |
| Comparator Product(s) | ACUVUE® OASYS for ASTIGMATISM with HYDRACLEAR® PLUS contact lenses (AOFAHP; senofilcon A) |
| Planned Duration of Exposure | ~ 28 days total duration (test and comparator): Test Product: 14 (-0/+2) days Comparator Product: 14 (-0/+2) days |
| Visits | Visit 1: Screening/Baseline/Trial fit Visit 2: Dispense Lens 1 [3 – 4* days after Visit 1] Visit 3: Week 1 Follow-up Lens 1 [7 -0/+ 1 days after Visit 2] Visit 4: Week 2 Follow-up Lens 1 [7 -0/+ 1 days after Visit 3] Visit 5: Dispense Lens 2 [2 (at least 48 hours) – 4* days after Visit 4] Visit 6: Week 1 Follow-up Lens 2 [7 -0/+ 1 days after Visit 5] Visit 7: Week 2 Follow-up Lens 2/ Exit [7 -0/+ 1 days after Visit 6] * Washout period with habitual spectacles only after Visit 1 and Visit 4 |

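### Minor: a 15% screening failure rate applied to about 92 consented subjects leaves about 78, not the 80 completers targeted; 92 is 80 × 1.15, whereas 80 / 0.85 is 94.1

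*Protocol*

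**What the plan says.** Protocol Section 8 sets out "approximately 92 volunteer subjects to be enrolled (consented) at approximately 6 sites within the US, with a target of 80 total completed subjects". It then explains the enrolment number: "A 15% screening failure rate is expected requiring approximately 92 subjects are expected to be enrolled". No other reason for the gap between 80 and 92 appears in the public text.

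Two definitions fix the base of the 15%:

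- **Enrolled means consented.** The Glossary defines an enrolled subject as "Any subject who signs an informed consent form for participation in the study", and Section 8.1 repeats it: "Upon signing informed consent, the subject is considered enrolled in the study".
- **Screen failures come after consent.** Section 10.4.1 describes them as "Subjects who were excluded from the study after signing the informed consent and prior to randomization to product/dispense of study product".

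SAP Section 1.2 (Table 1-1) carries the two counts without the rate: "Target to complete: 80 Planned to enroll: ~92".

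**The concern.** Section 8 gives three numbers (92 consented, 80 completed, 15% screen failure) and presents the third as the reason for the first. They do not fit together. Screen failures have already signed consent, so they are among the 92, and 15% of 92 is more than the 12 places by which 92 exceeds 80. The 92 looks like the result of adding 15% to the target instead of dividing the target by the proportion expected to pass.

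Little is at stake statistically. If 15% is a fair expectation, however, the study is planned to finish slightly below its own completer target with no fault in conduct, and the study report would have to explain a shortfall that came from the planning arithmetic.

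**Working it through.** **Inputs**

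- Planned consented: about 92 (Protocol Section 8; SAP Table 1-1)
- Target completed: 80 (same places)
- Expected screening failure rate: 15% (Protocol Section 8)
- Base of the rate: consented subjects (Glossary; Sections 8.1 and 10.4.1)

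**Step 1: reproduce the plan's figure.** Target × (1 + rate) = 80 × 1.15 = 92.0. This matches exactly, and it treats the 15% as a share of the 80.

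**Step 2: apply the rate to its proper base.**

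- Expected screen failures: 92 × 0.15 = 13.8
- Places available: 92 − 80 = 12
- Expected to pass screening: 92 × 0.85 = 78.2
- Shortfall: 80 − 78.2 = 1.8 subjects, or 1.8 / 80 = 2.25% of the target

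**Step 3: invert correctly.** Target / (1 − rate) = 80 / 0.85 = 94.1. Check: 94 × 0.85 = 79.9 and 95 × 0.85 = 80.75, so 95 is the first whole number whose expectation reaches 80.

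**Step 4: find the rate that 92 and 80 do support.** 12 / 92 = 13.0%, whereas 12 / 80 = 15.0%. The stated 15% is the second ratio.

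**Step 5: compare with chance variation.** Assume that subjects pass screening independently with probability 0.85. The number passing out of 92 then has mean 78.2 and SD √(92 × 0.85 × 0.15) = 3.42. The exact binomial chance that at least 80 pass is 0.36.

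**Step 6: consider loss after randomisation.** The visible text gives no dropout rate, and Section 10.4.2 rules out replacing discontinued subjects. The rates below are assumptions for illustration only.

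| Assumed dropout after randomisation | Expected completers, 92 × 0.85 × (1 − dropout) |
|---|---|
| 0% | 78.2 |
| 2% | 76.6 |
| 5% | 74.3 |
| 10% | 70.4 |

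Any such loss widens the gap.

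**The case against.** The best case against raising this is that it is immaterial, and most of that case stands.

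- **The counts are approximate.** Both documents mark 92 as approximate, and 92 is only about 2% below 94.1. This is true of the size of the gap. It does not explain the sentence, because the stated reason leads to 94 or 95, and the exact match with 80 × 1.15 points to the wrong base and not to rounding.
- **No analysis depends on it.** The protocol says "No inferences are to be made on the primary effectiveness endpoint; therefore, no hypotheses are formulated", and the SAP Executive Summary says "Decision criteria for study success are not applicable for this study". The primary endpoint is read 10 minutes after insertion at the dispense visit in the full analysis set, so the number of completers is not its denominator. This stands in full and is why the point is minor.
- **80 can still be reached.** This also stands. The 36% chance needs care: it concerns passing screening, not completing, and it treats 92 as a hard cap. By the same calculation 94 gives 56% and 95 gives 65%, so much of the risk comes from having no margin at all.
- **Text that is not public might explain the numbers.** No sample-size section is visible in either document, and the synopsis row on the subject population is cut off. A dropout allowance there could not rescue 92, however, because screen failure alone already takes more than the 12 spare places.
- **The documents do not show which of the three figures is wrong.** This is fair. The conflict arises in the sentence that links them, and the sponsor must decide which figure governs.

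**Conclusion.** The concern holds as a minor arithmetic error in Protocol Section 8. At the stated 15% screening failure rate, about 92 consented subjects yield an expected 78.2, which is 1.8 (2.25%) below the target of 80 even if nobody is lost afterwards. The conclusion rests only on the protocol's own definitions of enrolment and screen failure. The 36% chance also assumes that subjects pass screening independently.

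No power is lost and no planned result changes. SAP Table 1-1 is not inconsistent in itself, because it gives 80 and 92 without the rate that brings them into conflict. Confidence is high on the arithmetic.

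**What to change.** Reconcile the three figures in Protocol Section 8 without enrolling more subjects. The sponsor can choose between two options.

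1. **Keep 92 and 15%, and restate the yield.** Say that about 92 consented at 15% screen failure gives about 78 randomised, and so at most about 78 expected completers. Align the 80 in SAP Table 1-1. This keeps the sponsor's stated screening expectation.
2. **Keep 92 and 80, and replace the rate.** Say that the plan can absorb a loss of about 13% from all causes (12/92; 92 × 0.87 = 80.04). This 13% is derived from the two counts and is not an observed or expected rate, so the text should call it the loss the plan can bear. If 15% screen failure is still expected, option 1 is the more candid.

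Consenting 94 or 95 would also make the arithmetic work, but it adds subjects for a gap that affects no analysis.

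The cost is a text edit only. Option 1 edits Section 8 and SAP Table 1-1; option 2 edits one sentence in Section 8 and leaves the SAP as it is. Any other place that repeats the counts needs the same edit. The protocol synopsis should be checked, since its subject population row is incomplete in the public text.

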## 8.1 Inclusion Criteria

Written informed consent must be obtained before any study specific assessment is performed. Upon signing informed consent, the subject is considered enrolled in the study.

Subjects eligible for inclusion in this study must fulfill **all** of the following criteria:

1. Subject must be at least 18 years of age.
2. Subject must be able to understand and must sign an informed consent form (ICF) that has been approved by an Institutional Review Board (IRB/IEC).
3. Successful wearers of any commercial toric soft contact lenses (except AOfAHP and daily disposable lenses) in both eyes with at least 3 months wearing experience, with a minimum wearing time of 5 days per week and 10 hours per day.
4. BCVA distance (as determined by manifest refraction at screening) 20/25 or better in each eye with a sphero-cylindrical refractive error within the available study lens parameter range in the study.

Note: Study lens parameters available in this study are:

-0.75 D and -1.25 D cylinder power with:

- (a) -0.25 to -4.00 D (in 0.25 D steps) spherical power in 10°, 90°, 170° and 180° axis as available
- (b) -5.00 to -10.00 D (in 1 D steps), -5.50 D & -6.50 D spherical power in 90° and 180° axis as available
- (c) +1.00 to +8.00 D (in 1 D steps) spherical power 90° and 180° axis as available

5. Distortion-free keratometric readings at screening

6. Subject must possess spectacles (with 0.3 logMAR or better vision OU) and be willing to wear habitual spectacles for vision correction when study lenses are not worn, as needed.
7. Subject must be willing to stop wearing their habitual contact lenses for the duration of study participation.

9. Willing to NOT use rewetting/lubricating drops at any time during the study.
10. Subjects must be willing and able to attend all scheduled visits.

